11.1.5.2 Pharmacokinetic Assessment Sampling and Processing

For all subjects, blood samples for the determination of plasma total Mo will be collected and processed at scheduled time points as delineated in the Study Events Flow Chart (Section 6). A total of approximately 1512 samples (84 per subject) will be collected for PK analysis as per the target sample times (times blood will be drawn in relation to dosing).

The exact time points for collection of PK samples may be amended following evaluation of the data from the ongoing Study WTX101-101. If this is required it will be confirmed prior to study start. However, the total volume of blood taken for PK sample analysis will not be increased from that stated in Section 11.1.5.3.

Details on the sample collection process will be included in the central laboratory manual. The predose blood sample should be taken within 60 minutes prior to dosing. Samples up to and including the 8 hour postdose samples will be collected within 3 minutes of the scheduled time, thereafter all postdose samples will be collected within 30 minutes of the scheduled time. The actual blood collection date and time will be recorded in the source documents. All deviations outside the range allowed above will be documented as protocol deviations. In all such cases, appropriate time corrections, for the actual time of sample collection will be incorporated at the time of data analysis.

The actual sample date and times (date and times samples actually taken) will be recorded in the source notes and will be entered at the time of or as soon as possible after sampling. All times must be recorded in the 24 hour format. An explanation must be given for any blood sample taken outside of the set sampling times.

Sample Processing: The Sponsor will provide a laboratory manual that will detail the handling of PK blood samples.

Analytical Methodology: Plasma samples will be assayed by a validated inductively coupled plasma mass spectrometry (ICP-MS) method, which is specific for the determination of Mo. A validation study will be conducted by the appointed bioanalytical laboratory to establish validity. This study will be appended to the final report.

Samples from all subjects enrolled in the study including drop-outs for AEs will be analyzed. The criteria for repeat analysis as defined in the respective in-house procedure will be followed.

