Key Assessments:	Pharmacokinetics:The plasma concentrations of WTX101 will be measured by plasma concentrations of total elemental Mo.The following PK parameters will be calculated for total Mo in plasma: AUC _{0-t} , AUC _{0-inf} , C _{max} , t _{max} , λz , t _{1/2} , CL/F, and Vz/F. Descriptive statistics will be computed for all parameters. The parameters C _{max} , AUC _{0-t} , and AUC _{0-inf} will be compared among treatments using an analysis of variance (ANOVA) on the In- transformed values. T _{max} will be compared among treatments using non-parametric statistic, i.e. Wilcoxon Rank Sum.	
	Safety: Safety will be monitored through physical examinations, vital sign measurements, electrocardiograms (ECGs), AEs and clinical laboratory tests. Summary statistics for the laboratory safety tests, ECGs, and/or vital signs will be computed and provided.	

WTX101 EC Drug Absorption and Food Effect Study Protocol Wilson Therapeutics

Sponsor Project No.: WTX101-102 Celerion Project No.: CA13895 US IND No.: 119,006

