8.2.3 Rationale for Endpoints

The primary endpoints will be the AUCs and C_{max} , as these PK parameters are the most relevant to characterize the rate and extent of exposure following WTX101 administration - from the treatments to be tested.

Other parameters will also be presented, including: t_{max} , λz , and $t_{\frac{1}{2}}$, CL/F, and Vz/F.

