In each of the 3 periods, all subjects (Treatments A, B, and C) will be admitted to the CRU on Day -1, and will receive WTX101 EC tablet alone under fasting conditions (Treatment A); WTX101 EC tablet under fed conditions (Treatment B); or, omeprazole under fasting conditions followed by WTX101 non-coated capsule under fasting conditions (Treatment C). PK sampling will be obtained at the following timepoints while subjects remain in the CRU: Time 0 (within 1 hour predose), and then 1, 2, 3, 3.5, 4, 4.5, 5, 6, 7, 7.5 8, 8.5, 9, 9.5, 10, 12, 14, 16, 24, 36, and 48 hours postdose. Subjects will be discharged on Day 3 following the 48 hours postdose procedures, unless medically necessary to extend confinement to 72 hours.

Subjects will be required to return to the CRU for outpatient visits on 6 consecutive days (Days 4, 5, 6, 7, 8 and 9) in each period, for subsequent PK sampling and procedures at: 72, 96, 120, 144, 168, and 192 hours postdose.

Dose regimens are described as follows:

- Treatment A: 60 mg WTX101 (2 x WTX101 EC tablets, 30 mg) at Hour 0 on Day 1 following an overnight fast.
- Treatment B: 60 mg WTX101 (2 x WTX101 EC tablets, 30 mg) at Hour 0 on Day 1, 30 minutes after the start of a high-fat breakfast, preceded by an overnight fast.
- Treatment C: 20 mg omeprazole (1 x 20 mg delayed-release capsule) QD in the morning of Days -5 to -1 following an overnight fast, 20 mg omeprazole delayed-release capsule at Hour -1 on Day 1 following an overnight fast, and 60 mg WTX101 (2 x WTX101 non-coated capsules, 30 mg) at Hour 0 on Day 1.

Appropriately trained employees of the study site will administer the study treatment. Each dose will be administered with approximately 240 mL of room temperature water. The date and time of administration will be recorded in the source notes and witnessed by a second person from the clinical facility.

The washout between WTX101 doses in each period will be at least 14 days.

Subjects will return to the CRU approximately 14 days (+/-2 days) after the final study medication administration for an end-of-study (EOS) visit with follow-up procedures, and to determine if any AE has occurred since the last study visit. Subjects who terminate the study early should be seen and assessed by an Investigator, whenever possible, to undergo the procedures associated with the EOS visit.

Subjects may be replaced at the discretion of the Sponsor.

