11 STUDY PROCEDURES

The Study Events Flow Chart (Section 6) summarizes the clinical procedures to be performed at each visit. Individual clinical procedures are described in detail below. Additional evaluations/testing may be deemed necessary by the PI and/or the Sponsor for reasons related to subject safety.

For this study, the blood collection for total Mo is the critical parameter and needs to be collected as close to the exact time point as possible. All other procedures should be completed as close to the prescribed/scheduled time as possible, but can be performed prior or after the prescribed/scheduled time.

Any nonscheduled procedures required for urgent evaluation of safety concerns take precedence over all routine scheduled procedures.

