11.1.3 Vital Signs

Single measurements of body temperature, respiratory rate, blood pressure and heart rate, will be measured as outlined in the Study Events Flow Chart (Section 6).

Blood pressure and heart rate measurements will be performed on subjects after at least 2 minutes in the supine position. Vital signs may be taken at any other times, if deemed necessary. Additional blood pressure and heart rate measurements will be performed with subjects in a supine position except when subjects are reclined, semi-reclined or in a seated position because of study procedures and/or AEs (e.g., nausea, dizziness) or if deemed necessary by the PI.

Blood pressure and heart rate will be measured within 2 hours prior to Day 1 dosing of each period for the predose time point. Postdose vital signs will be performed within approximately 10 minutes of the scheduled time point.

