11.1.4 ECG Monitoring

Single 12-lead ECGs will be performed as outlined in the Study Events Flow Chart (Section 6).

ECGs will be performed on subjects after at least 2 minutes in supine position. All ECG tracings will be reviewed by the Study Physician or his/her designee. The following ECG variables will be collected and transcribed into the eCRF; HR, PR interval, QRS duration, QT interval, QTcB interval, QTcF interval and overall interpretation

ECGs will be measured within 2 hours prior to Day 1 dosing of each period for the predose time point. When scheduled, postdose ECGs will be performed within approximately 20 minutes of the scheduled time point.

A subject will be withdrawn from the study by the Study Physician if, in their medical judgment, ECG findings are present which make continued study participation not in the subject's best interest.

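### The PK sampling window widens from ±3 to ±30 minutes inside the half-hourly block at 7–10 h, so the planned spacing after 8 h is not secured (minor, nearly free to fix)

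*Protocol*

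**What the plan says.** Section 11.1.5.2 sets two tolerances for postdose PK samples. The first is tight: "Samples up to and including the 8 hour postdose samples will be collected within 3 minutes of the scheduled time". The second covers everything later: "thereafter all postdose samples will be collected within 30 minutes of the scheduled time". Nothing elsewhere in the protocol gives the samples just after 8 h a narrower limit.

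The in-house schedule in Section 10.1 (also the Synopsis and the flow chart in Section 6) has draws at 7, 7.5 and 8 h and continues "8.5, 9, 9.5, 10, 12, 14, 16, 24, 36, and 48 hours postdose". The half-hourly block thus runs from 7 to 10 h, and the change of tolerance falls in its middle.

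Section 11 ranks the PK draw above other procedures: "the blood collection for total Mo is the critical parameter and needs to be collected as close to the exact time point as possible". The numerical limits for two of those other procedures are nevertheless tighter than the PK limit after 8 h. Section 11.1.3 says "Postdose vital signs will be performed within approximately 10 minutes of the scheduled time point", and Section 11.1.4 says "postdose ECGs will be performed within approximately 20 minutes of the scheduled time point".

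On endpoints, Section 8.2.3 makes the AUCs and Cmax primary because "these PK parameters are the most relevant to characterize the rate and extent of exposure". It places tmax among the other parameters, whereas Section 9.2 includes tmax in the primary endpoint list. The Synopsis adds that tmax "will be compared among treatments using non-parametric statistic, i.e. Wilcoxon Rank Sum".

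**The concern.** A tolerance as wide as the spacing between samples does not secure that spacing. Up to 8 h the collection rule protects the half-hourly resolution; from 8.5 h the same planned resolution has no protection. Two consecutive samples could be drawn almost together, or an hour and a half apart, and both would count as on time.

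If a subject's concentration peaks between 8 and 10 h, the observed Cmax and tmax depend on where the draws happened to fall. Recording actual times corrects the time axis but cannot supply a concentration that was not measured, so no later analysis plan can repair this. Which time is used in the analysis for in-window samples is a separate matter, left to the pharmacokinetic analysis plan, and is not part of this point.

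**Working it through.** **The plan's own count.** Per period there is 1 predose sample, 21 in-house postdose samples and 6 outpatient samples: 28. Over 3 periods that is 84 per subject, and over 18 subjects 1,512. Both figures match Section 11.1.5.2. The affected samples (8.5, 9, 9.5 and 10 h) are 4 per period and 4 × 3 = 12 of 84 per subject.

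**Allowed windows.** At ±30 minutes: 8.0–9.0, 8.5–9.5, 9.0–10.0 and 9.5–10.5 h.

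**Allowed gaps.** Gap limits = planned gap ± (sum of the two half-windows). Overlap = sum of the half-windows − planned gap. A negative lower limit means the order could reverse; with order kept, the gap is bounded at 0.

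| Pair | Planned gap (min) | Half-windows (min) | Allowed gap (min) | Overlap (min) |
|---|---|---|---|---|
| 7/7.5 and 7.5/8 h | 30 | 3 + 3 | 24 to 36 | none |
| 8/8.5 h | 30 | 3 + 30 | 0 (−3) to 63 | 3 |
| 8.5/9, 9/9.5 and 9.5/10 h | 30 | 30 + 30 | 0 (−30) to 90 | 30 |
| 10/12 h | 120 | 30 + 30 | 60 to 180 | none |

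With ±3 minutes through 10 h, every pair from 7 to 10 h has a gap of 24–36 minutes, and 10/12 h has 120 ± 33 = 87–153 minutes. With ±10 minutes at 8.5–10 h, the pairs from 8.5 to 10 h have gaps of 30 ± 20 = 10–50 minutes.

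**Size of effect, by simulation.** The protocol gives no expected tmax or rate constants, so all inputs here are assumptions:
- one-compartment curve with first-order absorption, ka 0.5–2 per hour, ke 0.03–0.1 per hour;
- lag chosen so that the true peak is uniform in 8.5–10 h;
- each draw uniform within its allowed window, and actual times used;
- postdose schedule from 1 to 24 h, 200,000 profiles per setting.

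| Quantity | Current | ±10 min to 10 h | ±3 min to 10 h |
|---|---|---|---|
| SD of tmax error (h) | 0.23 | 0.16 | 0.15 |
| Mean Cmax loss, ka 1 | 0.08–0.26% | – | 0.03–0.11% |
| Mean Cmax loss, all settings | 0.04–0.51% | – | 0.02–0.21% |
| Median longest gap between draws, 8–10 h (h) | 0.89 | – | 0.55 |
| Longest gap over 1 h | 29% of profiles | – | 0% |

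**Sensitivity to the assumptions (ka 1, ke 0.1).**
- Peaks spread over 5–10 h instead of 8.5–10 h: the tmax SD moves only from 0.24 to 0.22 h.
- Peaks at 3–5 h or 7–8 h: no difference between the two rules.
- Draws centred on the scheduled time (triangular over ±30 minutes): longest gaps over 1 h fall from 29% to 11% of profiles.
- Staff staying within ±10 minutes anyway: the gain from a formal ±3 minutes is 0.16 to 0.15 h.

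**The case against.** The strongest reply is that the schedule accepts worse elsewhere. With peaks at 5–7 h, where draws are hourly and the window is already ±3 minutes, the same model (ka 1, ke 0.1) gives a tmax error SD of 0.29 h and a mean Cmax loss of 0.41%. Peaks at 8.5–10 h under the ±30-minute rule give 0.23 h and 0.26%. This stands, and it caps the importance of the point. It does not explain why half-hourly draws were planned to 10 h and then protected only to 8 h.

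Second, the gain is slight for the primary parameters: at ka 1 per hour, 0.05 to 0.16 percentage points of Cmax. For tmax, if the within-subject SD is 1–2 h (an assumption), moving the error SD from 0.23 to 0.146 h cuts the total SD by 1.5% to 0.4%: √(1² + 0.23²) = 1.026 against √(1² + 0.146²) = 1.011, and 2.013 against 2.005. This stands too.

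Third, Section 11 already tells staff to draw as near to the nominal time as they can, subjects are confined, and actual times are recorded. Uniform draws over an hour are therefore a pessimistic scenario, not a forecast. That is fair, but the instruction sets no limit: the only number that triggers a deviation is 30 minutes.

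Fourth, the vital-sign and ECG tolerances are approximate, and Section 11 lets those procedures move around the PK draw. That comparison is supporting colour, not the basis of the point.

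**Conclusion.** The point holds as a minor design flaw. The overlap is arithmetic and rests on no assumption: three adjacent pairs overlap by 30 minutes and the 8/8.5 h pair by 3 minutes, so the half-hourly spacing from 8 to 10 h is planned but not enforced.

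The consequence rests on assumptions about the curve, the location of the peak and staff behaviour. At the pessimistic end it is an extra 0.08 h or so in the SD of the tmax error and a few tenths of a percent in Cmax. If peaks come before 8 h it is nil, and if staff already draw promptly it is close to nil. The comparisons of AUC and Cmax between treatments are not at risk. The case for change is that the remedy is nearly free and makes 12 draws per subject deliver the spacing they were scheduled for.

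**What to change.** In Section 11.1.5.2, extend the ±3-minute window so that it runs through the 10 h postdose sample, and keep ±30 minutes from 12 h onward. Any window below ±15 minutes for the 8.5, 9, 9.5 and 10 h samples would also remove the overlap; ±10 minutes is a workable alternative. If the time points are amended after the data from Study WTX101-101 are seen, set each window to less than half the new spacing.

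The cost is one sentence. Subjects are in the unit until 48 h and actual times are already recorded for every sample, so no visit, sample or blood volume is added. The only downside is a few more minor timing deviations to log.

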11.1.5.3 Blood Volume Drawn for Study Assessments

Table 1 Blood Volume during the Study

Sample Type	Number of Timepoints	Approximate Volume per Time Point * (mL)	Approximate Sample Volume Over Course of Study (mL)		
Screening laboratory safety tests (including hematology, serum chemistry, serology, Cp, and Cu), FSH (for postmenopausal female subjects only) and serum pregnancy (for female subjects only).	1	23	23		
On-study hematology	7	4	28		
On-study serum chemistry and serum pregnancy (for female subjects only) when scheduled at the same time	7 8.5		59.5		
PT, INR, and aPTT	8 4.5		36		
Blood for total Mo (PK)	84	6	504		
Total Blood Volume (mL)→ 650.5**					

** Additional volume, up to 50 mL may need to be collected due to unforeseen circumstances.

11.1.6 Adverse Events

11.1.6.1 Adverse Event Definition

Adverse Event (AE): Any untoward medical occurrence in a clinical investigation subject administered a pharmaceutical product and which does not necessarily have a causal relationship with this treatment. An AE can therefore be any unfavorable and unintended sign (including an abnormal laboratory finding), symptom, or disease temporally associated with the use of a medicinal (investigational) product, whether or not related to the medicinal (investigational) product.

11.1.6.2 Monitoring

Subjects will be monitored throughout confinement, and also during a home omeprazole dosing, for adverse reactions to the study formulations and/or procedures. At the time of release, subjects will be asked how they are feeling. At the time of subsequent sample collections in each study period and at the beginning of the second and third period subjects will be queried with an open-ended question such as: 'How have you been feeling since your last visit?'

All symptoms will be evaluated by the PI before the next dose is administered.

Regardless of the relationship of the AE to the study drug the AE must be recorded in the eCRF. Any subject who reports an AE (whether serious or non-serious) or has a clinically significant abnormal laboratory test value(s) will be evaluated by the PI and will be treated and/or followed up until the symptoms or value(s) return to normal, or acceptable levels, as

judged by the PI. Treatment of serious adverse events (SAEs) will be performed by a physician, either at Celerion or at a nearby hospital emergency room. Where appropriate, medical test(s) and/or examination(s) will be performed to document resolution of event(s). Outcome may be classified as resolved, improved, unchanged, worse, fatal or unknown (lost to follow-up).

11.1.6.3 Reporting

AEs (including SAEs) will be recorded beginning with the first dose of study medication, either omeprazole or WTX101 (as per randomization), and through the EOS visit. AEs will be followed for 14 days after the last dosing with WTX101; or until the event resolves or stabilizes, whichever is earlier. All AEs that occur during this period will be recorded.

The PI will review each event and assess its relationship to drug treatment (likely, probably, possibly, unlikely or unrelated). Each sign or symptom reported will be graded on NCI CTCAE toxicity grading scale 5-point severity scale (Grade 1, 2, 3, 4 and 5).⁸

AE Severity	Definition
Grade 1	Mild; asymptomatic or mild symptoms; clinical or diagnostic observations only; intervention not indicated
Grade 2	Moderate; minimal, local or noninvasive intervention indicated; limiting age-appropriate instrumental ADL*
Grade 3	Severe or medically significant but not immediately life-threatening; hospitalization or prolongation of hospitalization indicated; disabling; limiting self-care ADL**
Grade 4	Life-threatening consequences; urgent intervention indicated
Grade 5	Death related to AE

The following definitions will be used for rating the severity of AEs:

Note 1: A semi-colon indicates 'or' within the description of the grade.

Note 2: Activities of Daily Living (ADL)

*Instrumental ADL refer to preparing meals, shopping for groceries or clothes, using the telephone, managing money, etc.

**Self-care ADL refer to bathing, dressing and undressing, feeding self, using the toilet, taking medications, and not bedridden.

The date of onset, time of onset, and outcome of each event will be noted. Additional variables to be recorded are as follows:

- Date and time when the AE started and stopped
- Maximum intensity
- Action taken
- Whether or not the AE is serious

- Whether or not the AE caused the subject to discontinue the study
- Outcome

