10.1.1 Confinement and Return Visits

During each of the 3 periods, subjects will be housed from at least 10 hours before dosing until after the 48-hour blood draw on Day 3. At all times, a subject may be required to remain at the CRU for longer at the discretion of the Principal Investigator (PI). Subjects will return for 6 consecutive days (Days 4, 5, 6, 7, 8 and 9) for the subsequent PK sampling. A final return visit will be required 14 days (+/-2 days) following the final administration of WTX101 for conduct of EOS procedures.

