10.1.2 Study Duration

Subjects who complete the study may be involved in the study for up to 48 days excluding screening (Day -5 of period 1 to the EOS visit). The entire study is expected to last approximately 48 days from the first subject dosed (Omeprazole) to last subject-last visit (LSLV).

The study has a screening phase (Day -28 to Day -5 of Period 1); three study periods (Periods 1, 2, and 3 comprised of Day -5 to Day 9); and an EOS visit 14 days (+/-2 days) following the final study medication administration. There is a 14 day minimum washout period between each dose of WTX101.

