11.1.5 Blood Sampling for Safety and Pharmacokinetic Analyses

11.1.5.1 Safety Laboratory Tests

All tests listed below will be performed as per Study Events Flow Chart (Section 6). Clinical laboratory results will be used during screening by the PI to establish eligibility for enrollment. Any deviation in laboratory values that are confirmed on re-examination to be clinically significant by the PI that would jeopardize the safety of the subject or impact the validity of the study results will result in exclusion of that subject. In addition, laboratory safety tests may be performed at various unscheduled time points, if deemed necessary by the PI.

Hematology

- Hemoglobin
- Hematocrit
- Total and differential leukocyte count
- Red blood cell count
- Platelet count

Urinalysis

- pH
- Specific gravity
- Protein***
- Glucose
- Ketones
- Bilirubin
- Blood***
- Nitrite***
- Urobilinogen
- Leukocyte esterase***

Serum Chemistry*

- Blood urea nitrogen (BUN)
- Bilirubin (total and direct)
- Alkaline phosphatase
- Aspartate aminotransferase
- Alanine aminotransferase
- Albumin
- Sodium
- Potassium
- Chloride
- Glucose (fasting)
- Creatinine**

Additional Tests

- HIV test
- HBsAg
- HCV
- Urine drug screen
 - Opiates
 - Amphetamines
 - > Barbiturates
 - Benzodiazepines
 - Cocaine
 - Cannabinoids
- Urine alcohol screen
- Serum pregnancy test (for females only)
- FSH (for post-menopausal females only)
- Prothrombin Time (PT) / International Normalized Ratio (INR), and activated Partial Thromboplastin Time (aPTT)
- Cp (Screening)
- Total Cu (Screening)
- * Samples for serum chemistry will be obtained following a fast of at least 8 hours at screening, and of at least 6 hours at check-in. In case of dropouts, rechecks and postdose serum chemistry, subjects may not have fasted for 6 or 8 hours before the serum chemistry sample is taken.
- ** At screening, creatinine clearance will be calculated using Cockcroft-Gault formula.
- *** If urinalysis is positive for protein, blood, nitrite and/or leukocyte esterase, a

WTX101-102_CA13895_FINAL_Clinical Study Protocol_25 Feb 2014

microscopic examination (for red blood cells, white blood cells, bacteria, casts, and epithelial cells) will be performed.

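### Section 11.1.6.3 stops AE follow-up by day 14 after the last WTX101 dose, while 11.1.6.2 follows the same non-serious event with no time limit

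*Protocol*

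**What the plan says.** Section 11.1.6.3 (Reporting) first sets the recording window: from the first dose of omeprazole or WTX101 through the EOS visit. It then adds a separate rule on follow-up: "AEs will be followed for 14 days after the last dosing with WTX101; or until the event resolves or stabilizes, whichever is earlier". The next sentence reads "All AEs that occur during this period will be recorded". Among the variables required for each event is "Date and time when the AE started and stopped".

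Section 11.1.6.2 (Monitoring) covers every subject with an AE, serious or non-serious, or with a clinically significant abnormal laboratory value. Such subjects are to be treated and/or "followed up until the symptoms or value(s) return to normal, or acceptable levels", as judged by the PI. No calendar limit is given. The same section states: "Outcome may be classified as resolved, improved, unchanged, worse, fatal or unknown (lost to follow-up").

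Section 11.1.6.5 follows SAEs until they are stable or resolved, also without a limit. Section 10.3.4 sends discontinued subjects to section 11.1.6 as a whole, which contains both of the rules at issue.

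On timing, section 10.1.1 says "A final return visit will be required 14 days (+/-2 days) following the final administration of WTX101", and section 10.1.2 says "There is a 14 day minimum washout period between each dose of WTX101".

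**The concern.** Two adjacent sections fix different ends to follow-up of the same event. Under 11.1.6.3 follow-up ends at day 14 even if the event is neither resolved nor stable. Under 11.1.6.2 it goes on.

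Safety and tolerability is one of the primary objectives (section 9.1). Site staff who apply 11.1.6.3 as written may close an unstable event and record no stop date. Staff who apply 11.1.6.2 will carry on to resolution. Late follow-up could then differ between subjects according to which section was read, and whichever course is taken can be called a departure from the other section.

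**Working it through.** No figure in the protocol needs reproducing. The check compares the two rules and then counts days.

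**The rules side by side**

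| | 11.1.6.2 | 11.1.6.3 |
|---|---|---|
| Events covered | Any AE, plus clinically significant laboratory values | AEs (section 11.1.6.1 counts an abnormal laboratory finding as an AE) |
| Clinical end point | Normal, or acceptable to the PI | Resolved or stable |
| Calendar limit | None | 14 days after the last WTX101 dose |
| How combined | Not applicable | The earlier of the two |

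Take a non-serious event that on day 14 is unresolved, unstable and not acceptable to the PI. Section 11.1.6.2 requires follow-up to continue; 11.1.6.3 ends it. The clinical end points differ as well: a value that is stable but not acceptable to the PI is finished under one section and open under the other.

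**Where the limit bites**

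Inputs: minimum washout 14 days (10.1.2); EOS visit 14 ± 2 days after the last WTX101 dose (10.1.1); last PK return visit at 192 hours (10.1).

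- With minimum washouts, doses fall on study days 1, 15 and 29. The limit is 29 + 14 = day 43.
- For a completer, days available from each dose are:
  - Period 1: 43 − 1 = 42
  - Period 2: 43 − 15 = 28
  - Period 3: 43 − 29 = 14
- The last PK return visit is 192 / 24 = 8 days after the Period 3 dose, which leaves 14 − 8 = 6 days.
- From the EOS visit, days left = max(0, 14 − EOS day):

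| EOS day after last dose | 12 | 13 | 14 | 15 | 16 |
|---|---|---|---|---|---|
| Days of follow-up left | 2 | 1 | 0 | 0 | 0 |

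The 42 and 28 days apply only to completers. A subject withdrawn after Period 1 had the last dose in that period, so the limit is 14 days from it.

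**Why EOS matters**

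Table 1 in section 11.1.5.3 lists 7 on-study hematology draws. With the flow chart, this fits two per period plus EOS: 3 × 2 + 1 = 7. After the early Period 3 draw, the next scheduled safety laboratory test is therefore EOS itself. An abnormality first seen there has almost no follow-up under 11.1.6.3. Sections 8.1.2 and 8.1.3 name hematologic changes and transaminase elevations among the known effects. Those came from repeated dosing in patients, so they may be rare after single doses in healthy subjects.

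**The case against.** The best defense is that both rules can be obeyed together. Section 11.1.6.3 says when its own obligation ends and does not forbid further follow-up, so an investigator who continues under 11.1.6.2 breaches nothing. On this reading Monitoring is a duty of care and Reporting governs data capture, with day 14 a loose restatement of the nominal EOS day. The PI also decides what level is acceptable, the outcome categories allow for events that close unresolved, and "laboratory safety tests may be performed at various unscheduled time points, if deemed necessary by the PI".

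Part of this stands. The uncapped duty in 11.1.6.2 survives, which limits real harm, and the outcome field can describe an event that is still open. A 14-day limit for non-serious events after single doses could also be a legitimate sponsor choice if it were stated consistently.

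The conflict itself remains:

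- The recording window is already set by the preceding sentence. The disputed one speaks of following events and uses a clinical end point, so it is more than a recording rule.
- The split between care and data does not hold, because 11.1.6.2 also requires eCRF entry, documentation of resolution and classification of outcome.
- PI discretion settles what is acceptable. It gives no answer when the PI judges the event not acceptable on day 14.

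**Conclusion.** The concern holds as a minor but real contradiction that should be corrected. For a non-serious AE or laboratory abnormality still unresolved and unstable at day 14, 11.1.6.3 applied literally ends follow-up that 11.1.6.2 requires, and the protocol sets no order of precedence.

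The exposure is mainly events that begin late in Period 3 or are first found at EOS. The completer figures assume minimum washouts; longer washouts would lengthen only the Period 1 and 2 figures. How many of the 18 planned subjects would be affected cannot be derived from the protocol, and it may be none.

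What is at stake is late safety follow-up and completeness of the AE stop date.

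**What to change.** In section 11.1.6.3:

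1. Keep the first sentence, which records AEs through the EOS visit.
2. Replace the second with: *AEs and clinically significant laboratory values ongoing at the EOS or early termination visit, or at discontinuation if no such visit takes place, will be followed until they resolve, or stabilize at a level acceptable to the PI (see 11.1.6.2); SAEs are followed per 11.1.6.5.*
3. Reword the third so that its period is explicit: *All AEs that occur from the first dose of study medication through the EOS visit will be recorded.* Deleting it would also do, since it then repeats the first sentence. It should not stay as it is, because its reference to the period could be read as extending the recording of new AEs into open-ended follow-up.

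This removes the day-14 limit, aligns the two clinical end points, and leaves the recording window for new AEs unchanged. The cost is two sentences of protocol text and an occasional contact or repeat laboratory test after EOS, which 11.1.6.2 already requires.
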